We have recently completed preliminary open-label studies with FEAST, first at Columbia University, and then at the Medical University of South Carolina in Charleston (Nahas et al., 2013b). We have published the outcomes of the first 17 patients studied. One patient withdrew from the study after a single titration session. After the course of FEAST (median 10 sessions), there was a $46.1 \pm 35.5\%$ improvement in Hamilton Rating Scale for Depression (HRSD24) scores compared to baseline (33.1 ± 6.8 , 16.8 ± 10.9 ; $P < 0.0001$). Eight of 16 patients met response criteria ($\geq 50\%$ decrease in HRSD24) and 5/16 met remission criteria ($HRSD24 \leq 10$). Patients achieved full re-orientation (4 of 5 items correct) in 5.5 ± 6.4 min (median time = 3.6 min), timed from when their eyes first opened after treatment. We have now studied 18 more patients (see results below), and we are completing the study in the original IDE with another two more patients still to enroll.

This work allowed us to refine the treatment. For example, we selectively modified the electrode geometry to decrease interelectrode resistance. Additionally we

modified the titration schedule, now only administering a standard 800 ma ultrabrief pulse, and thus no longer titrating in the current domain.

II. Study Objectives

This study will provide preliminary evaluation of the following:

1. Further characterization of the efficacy of FEAST and the safety of the treatment.
 - a. The primary efficacy measure will be the 24-item Hamilton Rating Scale for Depression. The changes in these scores from before to immediately following the treatment course will be compared in patients treated with the FEAST methodology and matched to nonrandomized patients at our facilities who were treated with conventional ECT methods (ultrabrief right unilateral [RUL] ECT).
 - b. Acute and subacute cognitive side effects following FEAST will be assessed with a brief neuropsychological battery. The primary acute measures will be the time to return of orientation following seizure induction. The primary subacute measures will be assessment of retrograde amnesia for autobiographical information. The neuropsychological measures will be compared in the patients treated with the FEAST methodology (under this IDE) and matched (but nonrandomized) patients who are treated with conventional ECT methods (also covered under this IDE).

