The measures of Clinical Status and Characteristics in Table 3 are essentially unchanged since the original IDE. The cognitive battery is considerably reduced. This was done since the primary goal of this study is the comparison of the groups in EEG manifestations of seizure, with comparisons of efficacy and side effects secondary. Second, none of the dropped measures showed significant change with FEAST administration in our prior analyses, and the literature on traditional ECT has only shown persistent deficits for retrograde memory for autobiographical events ([name], 2014b). The measures that were retained serve a particular purpose: (1) the mMMS at baseline is used for sample characterization and matching of the two groups. A significant difference between the groups would denote an effect pertaining to global cognitive status. This is not expected. (2) Orientation recovery will be assessed at each treatment (but obviously not at preFEAST baseline). This measure has been extremely sensitive to differences in ECT treatment modalities (sine wave vs. brief pulse; ultrabrief vs. brief pulse, BL ECT vs. RUL ECT, etc.) and has been found to predict long-term deficits in autobiographical memory (Sabin et al., 1995b). We expect the FEAST group to manifest faster recovery of orientation than the UB RUL ECT group, even though the latter has manifested remarkably rapid recovery compared to other ECT modalities ([name] et al., 2008). (3) The most critical measure is the CUAMI-SF. This measure has repeatedly shown differences between modalities and has the strongest evidence for persistent deficit following ECT. While effects of UB RUL ECT on this measure have been slight (compared to retested normal controls), nonetheless we predict an advantage for FEAST in this measure of autobiographical amnesia. (4) The Attitudes Interview collects patient self-report on the effects of the treatment course on mood

and memory. A global assessment is given by the patient, akin to a clinical global impression (CGI) for each domain. Recent research has shown that these are the only self-report measures in the history of ECT research to show significant covariation with objective cognitive deficits and with type of ECT modality (Berman et al., 2008, Brakemeier et al., 2011b). We predict that the FEAST and UB RUL ECT groups will be equivalent in self-report of effects on mood, but the FEAST group will report less deleterious impact on memory.

B. 5a MRI scan

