FEAST and ultrabrief RUL ECT patients will be treated identically except as noted below. The traditional d'Elia electrode placement will be used for UB RUL ECT (American Psychiatric Association, 2001), with the frontotemporal electrode tangential to the midpoint of the line connecting the right auditory tragus and the canthus. The posterior electrode will be tangential to the vertex (midpoint of line connecting nasion and inion). Standard stainless steel 2" diameter electrodes will be used. If it is deemed that patients require a change in ECT modality, a switch to either brief pulse RUL or BL ECT will be implememnted, as clinically indicated.

B.8 Assessment of Efficacy

Clinician ratings. Instruments include the HRSD (24-item) (Hamilton, 1967), MADRS (Montgomery and Asberg, 1979), CGI (severity and improvement) (Guy, 1976), and the GAS (Endicott and Spitzer, 1978). A clinical evaluation team independently completes these scales on the basis of conjoint interviews, both at set time points (preECT baseline, 1-2 days after ECT termination) and the HRSD alone is also completed at spaced intervals (weekly during the ECT course). Interviews usually take place between 10 AM-12 PM to minimize variability due to diurnal variation.

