Self-Report ratings. The Inventory of Depressive Symptoms (IDS-SR) (Rush et al., 1985) is completed at baseline, and following completion of the course. This instrument has shown strong psychometric properties and is especially broad in its coverage of depressive symptoms. It has been used in many MDE treatment trials, including STAR*D (Rush et al., 2006).

B.9 Classification of Clinical Outcome and Dropout

Dropout. If, for any reason, there is a lapse of 3 scheduled treatments during a FEAST course (e.g., intercurrent illness, withdrawal of consent), the course is considered terminated. If, for any reason, the patient receives a prohibited psychotropic they are also considered to have dropped out. Patients who withdraw consent for research participation are immediately withdrawn from the research. The Principal Investigator or the Study Physician may withdraw a patient from the protocol at any time if it is deemed in the patient's interest to do so. Examples include emergence of a complicating medical condition, discovery of a previously undiagnosed exclusion criterion, etc.

Response Criteria. Remission is the categorical outcome that has precedence for efficacy determination. However, response status denotes that substantial, but incomplete, benefit has obtained. The a priori criteria for response are consistent across virtually all MDE clinical trials. Based on an assessment 1-2 days following ECT, patients are responders if they have a $\geq 50\%$ reduction in HRSD₂₄ scores relative to preECT baseline. All other patients are nonresponders.

Remission Criteria. Especially when ECT is the treatment modality, the goal is remission and not response (Thase, 2003, Paykel, 2002, McCall, 2014, McCall, 2013). Remitters in this study must satisfy final response criteria and have a 1-wk postECT HRSD ≤ 10 . The remitter criteria are stringent, given the use of the 24-item HRSD and the severity of illness at study entry.

B.10 Assessment of Function and Attitudes Toward Treatment

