Oreintation recovery time will be assessed at every treatment session. The most profound cognitive effects of ECT are expressed in the postictal period (Daniel and Crovitz, 1983a, Daniel and Crovitz, 1983b, [name], 1986a). The repeated assessment (every treatment) strongly enhances reliability of measurement, and allows for examination of progressive change over the treatment course (Calev et al., 1991a, Calev et al., 1991b, [name] et al., 1986). The measurement of orientation recovery has been particularly sensitive to variation in ECT electrode placement, waveform, and dosage. Further, it has been repeatedly found to be a potent predictor of the degree of retrograde amnesia following the ECT course, even in the long-term (Sobin et al., 1995b). Following seizure termination, orientation (5 items) is assessed continuously until the criterion for full recovery is met or 90 min elapse. The critierion for recovery is correct response to 4 of the 5 items. The 5 questions pertain to name, birth date, age, place, and day of the week.

The mMMS, Buschke Selective Reminding Test (BSRT) and CUAMI-SF will be administered at baseline and at follow-up (during the week following FEAST or UB RUL ECT). The modified form of the MMS provides a total socre of 57 (as opposed to 30 with the original version) and broader coverage of gross cognitive abilities (Mayeux et al., 1981, Stern et al., 1987). The primary use of the mMMS is sample characterization, especially since there is evidence that low baseline scores predict more severe short- and long-term retrograde amnesia (i.e., cognitively-compromised paitents are more vulnerable to the key adverse effect on memory) (Sobin et al., 1995a). No change is expected in mMMS scores in either group. However, as a safety measure, the two groups will be compared in change in mMMS scores to verify this assumption and assure that there was no change in global congitive status.

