The primary analysis for Hypothesis 4 will use all available HRSD₂₄ data (i.e., the intent-to-treat data) from the FEAST and UB RUL ECT samples. A random regression model will be used to examine the relationship between HRSD₂₄ scores and treatment group. Time will be the within-subjects repeated measures factor, site and treatment group the between-subjects factors, with medication-resistance classification and baseline HRSD₂₄ serving as covariates. All interactions with time will be modeled. In secondary analyses, we will also include age, gender, age-at-onset of illness, and duration of current episode as covariates, if pre-screening indicates utility. We will investigate whether HRSD₂₄ scores are linear in time or quadratic, cubic, or piece-wise linear (e.g., hockey-stick shaped). Indeed, in a study comparing several different statistical methods in their sensitivity to ECT treatment groups differences in rate of clinical improvement, we found that the HRSD₂₄ scores over time were frequently nonlinear (Nobler et al., 1997a). The type of analysis conducted on HRSD₂₄ scores will be repeated for secondary analyses with the MADRS, IDS-SR, and CGI-S.

FEAST and UB RUL ECT will also be compared in the categorical outcomes of final remission status (HRSD₂₄ of 10 or less at post-treatment) in a secondary analysis to gauge generality of the effect and clinical significance. Nominal logistic regression analysis will be used to compare the treatment groups in covariate-adjusted odds of remission. Remission status will be the dependent variable. The independent variables will be the treatment group indicator, along with site, medication resistance, and baseline HRSD₂₄.

Hypothesis 5. In two primary cognitive measures, orientation recovery time and CUAMI-SF scores, FEAST will have a significant advantage relative to UB RUL ECT.

The cognitive measures were described in Section B.12. Orientation time will be averaged within each patient across all treatments. An ANCOVA will be conducted on these values with Site and Treatment Group as between-subject factors, and age and number of treatments in the average as covariates. A similar ANOVA will be conducted on CUAMI-

SF scores, with Site and Treatment Group as between-subject factors, and age, number of treatments, and baseline CUAMI-SF score as the covariates.

Hypothesis 6. FEAST will have a significant advantage in the subjective global evaluation of the effects of ECT on memory.

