Patients in the comparison group are selected from those referred for ECT and scheduled to start with ultrabrief, right unilateral (UB RUL) treatment. This treatment is routine in the US and internationally, and is considered to manifest the least short- and long-term cognitive side effects compared to other ECT modalities. Participation in this protocol presents no additional risks.

D. Device and Site Safety

Several procedures will be in place to enhance safety in use of the device at the Institute of Psychiatry at MUSC and the two facilities at the GRU (Augusta, GA and Aiken, SC).

D.1 Controlled Access Area

The device will be used only in the dedicated area used for the delivery of ECT at the Institute of Psychiatry at MUSC on the fifth floor. When not in use, the Spectrum 5000Q FEAST device will be shut off and the room and suite housing it is locked. Identical precautions will be taken in the GRU ECT suites in Augusta, GA and Aiken, SC.

D.2 Device Calibration and Evaluation

All the quality control procedures recommended by the manufacturer in the testing and calibration of the Spectrum 5000Q will be followed, including verifying the correct operation of the circuitry that determine whether bidirectional or unidirectional stimulation is delivered. These assessments of device integrity and calibration will be conducted on each device at each site prior to first use and then again at least every 6 months.

D.3 Screening of Subjects Prior to Treatment

As described above, the screening assessment of potential subjects will identify and exclude from participation individuals with current or past medical conditions that may place them at increased risk for adverse effects from ECT or who are unlikely to benefit. Screening will involve physician evaluation, physical examination, and blood work.

D.4 Conduct of FEAST

The conduct of FEAST is detailed in Section IV.B.6. The procedures are described with respect to all aspects of the administration of FEAST, including management of concomitant medications, provision of anesthesia, stimulus dosing, physiological monitoring, and data logging. Prior to study initiation, training sessions will be held in the use of the Spectrum 5000Q FEAST device with all Study Psychiatrists. The study monitor and sponsor will regularly attend treatment sessions to document compliance with study procedures.

D.5 Adjustment of Stimulation Intensity to Individual Seizure Threshold

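### Hypothesis 5 averages orientation time over all treatments, and nothing says that the UB RUL course ends if a comparator is switched to another ECT modality

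*Combined protocol and SAP*

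**What the plan says.** Orientation recovery is one of two primary cognitive measures in Hypothesis 5. Objective 1b in Section II gives it the same standing: "The primary acute measures will be the time to return of orientation following seizure induction". IV.B.12 says of orientation that "recovery time will be assessed at every treatment session". IV.B.15 then builds the endpoint: "Orientation time will be averaged within each patient across all treatments". The ANCOVA has site and treatment group as factors, and age and the number of treatments averaged as covariates. It has no term for modality or for a switch.

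IV.B.7 states that "FEAST and ultrabrief RUL ECT patients will be treated identically except as noted below". One of the items that follow is: "If it is deemed that patients require a change in ECT modality, a switch to either brief pulse RUL or BL ECT will be" made where clinically indicated. IV.B.1 and IV.B.6 leave the comparators' treatment to routine practice. IV.C.5 describes them as patients "scheduled to start with ultrabrief, right unilateral (UB RUL) treatment".

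IV.B.9 lists what ends a course or counts as dropout. A change of modality is not on the list, and the lapse rule is worded for "a lapse of 3 scheduled treatments during a FEAST course".

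For FEAST, IV.B.6 (Number of Treatments) offers non-responders traditional ECT as a second, Mode 2 course, and IV.C.2 places that offer after the research phase.

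**The concern.** IV.B.5 describes orientation recovery as "extremely sensitive to differences in ECT treatment modalities (sine wave vs. brief pulse; ultrabrief vs. brief pulse, BL ECT vs. RUL ECT, etc". Ultrabrief versus brief pulse and bilateral versus unilateral are the two contrasts that an IV.B.7 switch creates. III.C.5 says that bilateral placement and wider pulses bring more intense cognitive side effects. Post-switch sessions are therefore likely to show slower recovery.

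If those sessions enter a comparator's average, the UB RUL mean rises in the direction that Hypothesis 5 predicts. The session-count covariate is not a remedy, because it records how many sessions were averaged and not which kind. The study is also meant to supply effect sizes for a later randomized trial (IV.B.15), so a mixed comparator mean would carry over into that trial's planning.

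**Working it through.** The plan states no power, effect size or switch rate for Hypothesis 5, so there is no figure to reproduce. The check has a reading part and an illustrative calculation.

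**Reading.**
- The averaging rule (IV.B.15) has no modality limit.
- The switch (IV.B.7) has no stated timing and no rule closing the UB RUL course.
- The dropout list (IV.B.9) does not remove a switched patient.
- The intent-to-treat statement (IV.B.15) covers efficacy only.
- FEAST rescue (IV.B.6, IV.C.2) follows the research phase, so a FEAST average holds FEAST sessions only.

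**Inputs from the documents.** 40 completers per group (IV.B.1). SD 7.5 min, from the pilot FEAST patients timed from stimulus delivery (III.D.6). Session mean 8.8, range 4-14 (III.D.6). Minimum of 6 treatments before stopping for limited improvement, with the same guidance for UB RUL (IV.C.3, item 5).

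**Assumptions.** 10-30% of comparators switch. Switchers have 6 UB RUL sessions and then 4 or 6 others, so 4/10 = 40% or 6/12 = 50% of their sessions are in another modality. Each such session takes 7.5 or 15 min longer. The session-count SD is 2.5. Tests are two-sided at 5%. There is no true FEAST difference.

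**Shift in the UB RUL mean** = switch fraction × post-switch share × extra minutes.
- Lowest: 0.10 × 0.40 × 7.5 = 0.30 min, or 0.30/7.5 = 0.04 SD.
- Highest: 0.30 × 0.50 × 15 = 2.25 min, or 2.25/7.5 = 0.30 SD.

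For scale, the standard error of an unadjusted difference is 7.5 × √(2/40) = 1.68 min, and the difference detectable with 80% power is 1.68 × (1.96 + 0.84) = 4.7 min. The only within-patient FEAST versus UB RUL contrast in the documents is 21.6 − 14.7 = 6.9 min, in one patient (III.D.6).

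**False FEAST advantage** (share of simulated trials significant in FEAST's favour; ANCOVA with group, site, their interaction, age and session count; 6,000 runs per cell; nominal 2.5%):

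| Switching | +7.5 min (6+4 / 6+6 sessions) | +15 min (6+4 / 6+6 sessions) |
|---|---|---|
| 10% | 3.7% / 3.7% | 4.9% / 5.7% |
| 20% | 4.6% / 5.2% | 10.0% / 10.2% |
| 30% | 6.8% / 7.0% | 16.4% / 16.6% |

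A repeat simulation agreed to within about one percentage point. As a hand check on the lowest cell, 1 − Φ(1.96 − 0.30/1.68) = 3.7%. Averaging only pre-switch sessions, at 20% switching, gives 2.4%.

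The 6+6 pattern shifts the mean more than 6+4 but barely raises the error rate. Part of the reason is that switchers with long courses differ in session count, so the covariate absorbs some of the shift. It does so by accident of course length and does not remove the bias.

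**The case against.** The strongest reply is that IV.B.7 describes the comparators' counterpart of Mode 2. It gives no timing, and its destinations (brief-pulse RUL or bilateral ECT) resemble those offered to FEAST non-responders. IV.C.3 applies the same stopping guidance to UB RUL. IV.C.4 describes completing the FEAST or UB RUL course, then the research assessments, then alternative treatment. On that reading the UB RUL course closes before any switch, and no foreign session enters the average. The simulated switch after six sessions falls exactly where stopping is already allowed, so it fits this reading as well.

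This reading is plausible, but no section states it. An analyst who follows IV.B.15 as written would pool the sessions. A reader might infer that the protocol establishes mid-course switching; it does not, and that timing is an inference.

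A second reply is that a fully literal reading of all treatments would also take in FEAST Mode 2 sessions. With equal switching in both groups the bias cancels: a simpler two-sample simulation gave 2.3-2.8%. But IV.C.2 puts those sessions after the research phase, and pooling them would leave both groups' averages mixed.

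Two further inferences go too far. The ictal EEG contrast might be thought equally biased. IV.B.13 says only that the recordings allow averaging across treatments, and the direction after a switch to brief-pulse RUL is unclear. The autobiographical memory interview and the second MRI might also be thought contaminated. IV.B.12 and IV.C.4 point to assessment after the UB RUL course and before alternative treatment, so they need a clarifying sentence at most.

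It also stands that this is a non-randomized, unmasked preliminary study whose cognitive comparison the protocol itself treats as rough.

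**Conclusion.** The concern holds in a conditional form. If a comparator is switched before the UB RUL course is closed, the averaging rule as written mixes modalities in one group only, and the bias favours FEAST on a primary cognitive measure. The documents neither confirm nor exclude such switches.

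The size cannot be fixed from the documents. It runs from negligible (0.3 min, about 4% false FEAST advantages) to material (about 2 min, about 16%). The upper end needs 30% switching and 15 extra minutes per post-switch session, which is twice the pilot SD. These figures do not show that a positive Hypothesis 5 result would be false. They show that the rule leaves an avoidable bias open. For the EEG, the same restriction is a precaution and not the correction of a demonstrated bias.

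**What to change.** In IV.B.15, Hypothesis 5, average orientation time only over sessions given in the study modality (FEAST or UB RUL), and count only those sessions in the number-of-treatments covariate. Report the all-sessions average as a sensitivity analysis.

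In IV.B.7, state that the UB RUL research course ends at the last UB RUL treatment, and that end-of-acute assessments are done before the first treatment in another modality. Apply the same session restriction to any cross-treatment averaging of the Hypothesis 2 EEG.

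The cost is a few sentences. Treatment parameters are already logged at each session (IV.B.6), and clinical care does not change. The downside is that switchers contribute fewer and earlier sessions. III.C.5 reports that orientation recovery speeds up over an ultrabrief RUL course, so early sessions may look slower. The session-count covariate should therefore stay.
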